5.1 Number of Patients

For the phase I portion, up to 18 patients will be enrolled in this study from approximately 2 to 4 study centers in the US. For the phase II portion, 36 patients will be enrolled from these centers.

Patients who are withdrawn from treatment during Cycle 1 for reasons other than toxicity during the phase I portion of the study will be replaced. Patients in the phase II portion of the study, beyond the Simon's two-stage threshold, who are not evaluable for response will be replaced; however, patients who receive at least 1 dose of study drugs, and have measurable disease on bone marrow exam or by biopsy-documented extramedullary tumor at baseline, will be used for futility analyses, including the Simon's two-stage response evaluation.

Duration of Study

Patients, including those who achieve a CR, may receive the combination until they experience disease progression. Patients will discontinue treatment if they have an unacceptable drug-related toxicity. The maximum duration of treatment, however, will be 12 months from Cycle 1 Day 1 (C1D1) unless it is determined that a patient would derive benefit from continued therapy beyond 12 months.

Patients will be followed for 30 days after the last dose of the combination, or to the start of subsequent anticancer therapy, whichever occurs first, to permit the detection of any delayed treatment-related AEs. All patients, including those patients no longer on treatment, will be assessed for survival. Patients who discontinue the study, regardless of reasons for discontinuation, will be followed for up to 12 months after discontinuation of the study drug for survival (every month until death), loss to follow-up, or withdrawal of consent for further follow-up. In addition, information on any subsequent anticancer therapies will be collected during the survival follow-up period. For patients who achieve CR but discontinue study treatment while still in remission, disease progression based upon available local data will also be collected during the survival follow-up period.

The final analyses for the clinical study report may be conducted after all patients enrolled in the study have had the opportunity to complete 3-4 cycles of combination therapy (while still not progressing).

It is anticipated that this study will last for approximately 24-32 months, including 9 to 12 months in the phase I portion, and 15 to 20 months in the phase II portion.

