5.3 Dose Escalation Rules and MTD Definition

Dose escalation will be determined based on the number of toxicities as noted by the algorithm noted in the following Figure 5-1.

Figure 5-1 Dose/Schedule Escalation Algorithm TAK-659 and

TAK-659/Ixazomib Clinical Study Protocol

If 2 or more patients in any dose level experience DLT, enrollment at that dose level will stop. Following consultation between the sponsor and investigators, either the previous dose level will be considered the MTD (if 6 or more patients have been studied at that dose level), the previous dose level will be expanded (if fewer than 6 patients have been studied at that dose level), or a dose level intermediate between the current and the previous dose level will be evaluated.

To define the Maximum Tolerated Dose (MTD), subjects will be evaluated for DLT following two cycles (56 days) of treatment. Decisions to move to next dose escalation cohort will not be made until all subjects complete 2 cycles of therapy at a given dose.

The MTD is defined as the dose level at which fewer than 33% of subjects experience a dose limiting toxicity (DLT), and specifically is the dose level at which less than 2 out of 6 subjects experience DLT. The minimal safe and effective dosing with pharmacodynamic and pharmacokinetic parameters pointing toward the goal of efficacy optimization, will be the recommended dose (RP2D) for the Phase II component of the study. To achieve this, the developing results of safety, tolerability, efficacy, PK and PD in each dose-escalation cohort will be reviewed in real time after each cohort, to determine whether maximal safety and evolving efficacy milestones will have been reached based on examination of two consecutive cohorts, when safety and tolerability measures are within criteria for each.

- The criterion for safety will be DLT <20% within the cohort.
- The criterion for tolerability will be the administration of >80% of expected dose within the cohort.
- The criterion for efficacy will be the dose with an estimation of greater or equal to 25% ORR in the Flt3 mutant cohort, or greater than or equal to 10% ORR in the Flt3 wild-type cohort.
- The criterion for optimizing PK will be: on day 1, equal or greater than 100ng/ml peak (Cmax) TAK-659, or its trough equal or greater than 15ng/ml; on day 15, peak at least 200ng/ml, trough at least 40ng/ml. On the other hand, the day 15 peak should be less than 400ng/ml, and trough should be less than or equal to 100ng/ml.

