- The criteria for defining an optimization of PD will be the reduction in more than one of the epigenetic drivers by 50%: JUN, ID1, β -catenin, HOXA 9/10, MEIS1 or rise by 50% of the epigenetic repressor RUNX3.

Subjects will initially be enrolled onto dose level 1. Three to six evaluable subjects will be enrolled at each dose level. All subjects assigned to a dose level must be followed for at least 2 cycles before dose escalation to the next cohort level can begin.

Note: Subjects not evaluable for DLT assessment (i.e. do not complete at least 1 cycle of therapy due to reasons other than toxicity) on the Phase I portion of the protocol will be replaced for determination of dose escalation.

The following rules will be followed:

- An initial three subjects will be enrolled in cohort 1. If all 3 subjects in cohort 1 complete 2 cycles of therapy without dose limiting toxicity (DLT), the study will proceed to enroll 3 subjects at cohort 2. If all 3 subjects in cohort 2 complete 2 cycles of therapy without DLT, the study will proceed to Phase II with the MTD of each drug established.
- Alternatively, if 1 of the first 3 subjects in any given dose cohort experiences DLT, an additional 3 subjects will be enrolled at that dose level. If only 1 of the total 6 subjects in a dose level experience DLT, the study will proceed to the next dose level as planned. If 2 of the total 6 subjects in any given dose cohort experience DLT, the next lower dose level will be explored and considered the maximum tolerated dose (MTD) if no more than 1 of 6 subjects experience a DLT. That dose will be recommended for the Phase II study.

Number of subjects with DLT at given dose level	Escalation decision
0 out of 3	Enter 3 subjects at the next dose level.
≥ 2 out of 3	Dose escalation will be stopped. This dose level will be declared the maximum administered dose . Three (3) additional subjects will be entered at the next lower dose level if only 3 subjects were treated previously at that next lower dose level.
1 out of 3	Enter at least 3 more subjects at this dose level: 
 • If 0 of these additional 3 subjects experience DLT, proceed to the next dose level. • If 1 or more of these additional 3 subjects experience DLT, then dose escalation is stopped and this dose is declared the maximum administered dose. Three (3) additional subjects will be entered at the next lower dose level if only 3 subjects were treated previously at that dose.

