5.4 Definition of Dose Limiting Toxicity

Toxicity will be evaluated according to the NCI CTCAE version 5.

DLT is defined as any of the following events occurring within the first 2 cycles that are considered by the treating physician to be at least possibly related to therapy with study drug(s). AEs in which the relationship to study drug cannot be ruled out should be considered possibly related to study drugs TAK-659 and/or Ixazomib.

- Prolonged myelosuppression with the persistence of \geq Grade 4 neutropenia or thrombocytopenia in the absence of leukemia (blast count <5% in bone marrow) at least 42 days after the initiation of therapy.
- Any Grade 3 or greater nonhematologic toxicity with the following exceptions:
 - Grade 3 nausea and/or emesis resolved to \leq Grade 1 or baseline in a week after the use of an optimal antiemetic regimen based on standard practice. The optimal antiemetic regimen is defined as an antiemetic regimen that employs both a 5-hydroxytryptamine 3 serotonin (5-HT3) antagonist and a corticosteroid given in standard doses and according to standard schedules. Grade 3 nausea, vomiting must not require tube feeding, total parenteral nutrition, or require prolonged hospitalization.
 - Grade 3 diarrhea that resolved to \leq Grade 1 or baseline in a week after receiving the maximal supportive therapy based on standard practice. Grade 3 diarrhea must not require tube feeding, total parenteral nutrition, or require prolonged hospitalization.
 - Brief (<1 week) Grade 3 fatigue.
 - Electrolyte abnormalities correctable within 72 hours

- Grade 3 or 4 tumor lysis syndrome if it is successfully managed clinically and resolves within 7 days without end-organ damage.
- Failure to administer $\geq 75\%$ of planned doses of the study drug due to TAK-659- or Ixazomib-related or possibly related hematologic (considered not related to leukemic infiltration) or nonhematologic toxicities.
- Other TAK-659- or Ixazomib-related Grade 2 or greater nonhematologic toxicities that, in the opinion of the investigator, require a dose reduction or discontinuation of therapy.
- Confirmed Hy's law/guideline cases of drug-induced liver injury: ALT or AST $>3\times$ upper limit of normal and total bilirubin $>2\times$ ULN, which is not cholestatic (ALT value \div ALT ULN) \div [Alkaline phosphatase value \div Alk phos ULN] $= <2$), and not caused by disease. This will require permanent drug discontinuation.

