13.4 Populations for Analysis

The populations used for analysis will include the following:

- **Safety population:** Patients who receive at least 1 dose of TAK-659 and Ixazomib will be used for all safety and analyses.
- **Pharmacokinetic population:** Patients who have at least one measurable post TAK-659 dose concentration.
- **Pharmacodynamics population:** Patients with sufficient dosing in Cycle 1 and sufficient pharmacodynamics data will be used for PD analyses.
- **Response-evaluable population:** Patients who receive at least 1 dose of study drugs, have measurable disease at baseline, and 1 postbaseline disease assessment will be used for analyses of response.
- **DLT-evaluable population:** the DLT-evaluable population is defined as all patients in the phase I portion of the study who either experience DLT during Cycle 1 or complete at least 75% of the planned doses of TAK-659 and Ixazomib within 2 cycles and have sufficient follow-up data to allow the investigators and sponsor to determine whether DLT occurred.

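### Sections 5.1, 5.3 and 13.4 conflict on which Phase I patients are DLT-evaluable and which are replaced, leaving a non-toxic exit early in Cycle 2 without a consistent rule

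*Combined protocol and SAP*

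**What the plan says.** **DLT window.** Section 5.4 states: "DLT is defined as any of the following events occurring within the first 2 cycles". For the MTD, Section 5.3 adds that "subjects will be evaluated for DLT following two cycles (56 days) of treatment". One DLT, prolonged myelosuppression without leukemia, is judged "at least 42 days after the initiation of therapy".

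**Replacement.** Section 5.1 replaces "Patients who are withdrawn from treatment during Cycle 1 for reasons other than toxicity" in Phase I. The note in Section 5.3 uses an i.e. to define subjects not evaluable for DLT as those who "do not complete at least 1 cycle of therapy due to reasons other than toxicity", and replaces them.

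**Evaluability for analysis.** Section 13.4 admits Phase I patients who either have a DLT during Cycle 1 or "complete at least 75% of the planned doses of TAK-659 and Ixazomib within 2 cycles", and who have enough follow-up data to decide whether a DLT occurred.

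**Gates.** Section 5.3 also says: "Decisions to move to next dose escalation cohort will not be made until all subjects complete 2 cycles of therapy at a given dose". It adds "All subjects assigned to a dose level must be followed for at least 2 cycles" before the next level opens, and it states cohort sizes in evaluable subjects.

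No section says how to handle a patient who leaves in Cycle 2 for a reason other than toxicity.

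**The concern.** The replacement rule runs on a one-cycle clock and the DLT count on a two-cycle clock. A patient can therefore be finished with treatment, have no DLT, fail the Section 13.4 definition, and still not be replaced. An exit near the start of Cycle 2 is foreseeable. The Phase I calendar places a response marrow on Cycle 1 Days 15–21 with results due before the next Day 1, and progression ends therapy (Section 6.4). A withdrawal recorded just before the turn of the cycle is replaced; one recorded just after it is not.

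At stake is the MTD/RP2D, the Phase I primary endpoint and the source of the Phase II dose. With three to six patients per level, the classification of one patient can change an escalation decision.

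**Working it through.** The plan gives no operating characteristics for its 3+3 rule, so there is no stated figure to reproduce.

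**Step 1: where the Section 13.4 threshold falls.** Two cycles contain 2 × 15 = 30 TAK-659 doses and 2 × 3 = 6 ixazomib doses. 75% is 22.5 and 4.5, so at least 23 and 5 doses.

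| Last dosing day (full dosing) | TAK-659 | Ixazomib | 75% met? |
|---|---|---|---|
| End of Cycle 1 | 15/30 (50%) | 3/6 (50%) | No |
| Cycle 2 Day 7 | 22/30 (73%) | 4/6 (67%) | No |
| Cycle 2 Day 8 | 23/30 (77%) | 5/6 (83%) | Yes |

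**Step 2: status of a patient who leaves for non-toxic reasons, without a DLT.**

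| Time of exit | 5.3 note | 13.4 | Replaced (5.1, 5.3)? |
|---|---|---|---|
| During Cycle 1 | Not evaluable | Not evaluable | Yes |
| After Cycle 1, before Cycle 2 Day 8 | Evaluable | Not evaluable | No |
| From Cycle 2 Day 8 | Evaluable | Evaluable if follow-up suffices | No |

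The middle row is the conflict.

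**Step 3: the effect if the 5.3 note governs.** The leaver then counts as DLT-free. The chance of escalating is P(0/3) + P(1/3) × P(0/3 in the next three). Assume that half of DLT risk falls in Cycle 2, so a patient seen through Cycle 1 only has half the DLT probability.

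True DLT rate 30%, all patients fully exposed:
- P(0/3) = 0.7³ = 0.343; P(1/3) = 3 × 0.3 × 0.7² = 0.441.
- P(escalate) = 0.343 + 0.441 × 0.343 = 0.494.

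One of the first three exposed for Cycle 1 only (probability 0.15):
- P(0/3) = 0.7² × 0.85 = 0.4165; P(1/3) = 2 × 0.3 × 0.7 × 0.85 + 0.15 × 0.7² = 0.4305.
- P(escalate) = 0.4165 + 0.4305 × 0.343 = 0.564.

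One such patient in each group of three: 0.4165 + 0.4305 × 0.4165 = 0.596. At a true rate of 35% the same three figures are 40%, 47% and 51%.

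**Step 4: sensitivity to the two unknown inputs.** Let p be the two-cycle DLT rate, s the share of it arising in Cycle 2, and d the chance of a non-toxic exit at the start of Cycle 2 among patients without a Cycle 1 DLT. The observed rate per patient is q = p(1 − s·d). For p = 33.3%, P(escalate) is 42.8% when d = 0, and otherwise:

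| s | d = 10% | d = 20% | d = 30% | d = 40% |
|---|---|---|---|---|
| 25% | 44.4% | 46.1% | 47.7% | 49.4% |
| 50% | 46.1% | 49.4% | 52.9% | 56.4% |
| 75% | 47.7% | 52.9% | 58.2% | 63.6% |

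The documents give neither s nor d; both ranges are assumptions.

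**Step 5: the effect if the gates govern.** A leaver can never complete two cycles, so read literally the next level cannot open. Nothing allows that patient to be replaced.

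**Step 6: the mirror-image gap in 13.4.** Take a patient with a DLT on Cycle 2 Day 3 who stops then: 18/30 (60%) and 4/6 (67%) doses. Section 5.4 counts that DLT. Section 13.4 excludes the patient, because the DLT was not in Cycle 1 and 75% was not reached.

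**The case against.** The strongest reply is that no text says a Cycle 2 leaver counts as DLT-free, and several places point the other way. Sections 5 and 5.2 expect the cohort to complete its second cycle before escalation. The first rule in 5.3 escalates only when all three subjects complete two cycles without DLT. Section 14.3 requires review of each subject's toxicity and DSMC approval before the next dosing step. This stands as far as it goes: a reader might infer that escalation is simply too easy, and the documents do not establish that. But the gates do not settle the matter. The decision table counts subjects, its 1-of-6 route does not repeat the two-cycle condition, and the only definition of non-evaluable in 5.3 keeps the leaver in the denominator.

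A reader might also infer that such a patient could never show the late myelosuppression DLT. That is not supported. Section 5.1 follows patients for 30 days after the last dose, so a last dose on Cycle 1 Day 15 gives follow-up to about Day 45, past Day 42, unless new anticancer therapy starts sooner. That DLT also requires marrow blasts below 5%, which a patient leaving with persistent leukemia would not normally meet. What is lost for certain is Cycle 2 exposure, not necessarily calendar follow-up.

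Finally, it is tempting to cite the 13 of 35 patients (37%) in C34002 who received three or more 28-day cycles (Section 1.4.6) as evidence of early drop-out. That figure does not measure non-toxic exit in Days 22–42. Of 33 discontinuations, 21 were for adverse events, leaving 33 − 21 = 12 for progression, withdrawal or other reasons at any time.

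**Conclusion.** The point holds as a conflict between stated rules. Sections 5.1 and 5.3 use a one-cycle criterion for evaluability and replacement, Section 13.4 uses a two-cycle dosing criterion, and DLTs are counted over two cycles. A non-toxic exit after Cycle 1 and before Cycle 2 Day 8 is classified in opposite ways and is not replaced.

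The consequence depends on which text is followed. Under the 5.3 note, escalation becomes easier: 49% to 56% at a true 30% DLT rate with one such patient in the first three and half of DLT risk in Cycle 2. At 33.3% it is 44% to 64% against 43%, for exit rates of 10–40% and Cycle 2 shares of 25–75%. The direction is firm on that reading; the size rests wholly on assumed inputs. Under the gates, the cohort stalls instead. Either way the team would have to improvise on a primary endpoint, so the text should be corrected before Phase I decisions depend on it.

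**What to change.** Use one DLT-evaluable definition in Sections 5.1, 5.3 and 13.4, matched to the two-cycle window:

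- Any patient with a DLT in Cycles 1–2 is evaluable and counted, whatever the dosing. This replaces the Cycle 1 limb of 13.4.
- A patient without a DLT is evaluable only if the 13.4 dosing and follow-up requirement over two cycles is met.
- A patient who misses that requirement for reasons other than toxicity is replaced.
- 3+3 counts use DLT-evaluable patients only.

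These changes must be made together. Restricting the counts to 13.4-evaluable patients while 13.4 still recognizes only Cycle 1 DLTs could drop a genuine Cycle 2 DLT, as in Step 6. In the same edit, reconcile the 56 days in 5.3 with the 21-day cycle, under which two cycles are 42 days.

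The cost is a few sentences, and occasionally one more Phase I patient and about six weeks (2 × 21 days) for that cohort. The cap of 18 equals 3 cohorts × 6, so it leaves no room for replacements if every cohort fills; state whether replaced patients count toward it.

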5.3.1 Number of treatment cycles

Given our experience with this sort of treatment algorithm, we will follow the cues previously established in the Sorafenib/Vorinostat/Bortezomib trial to determine the course.

We will follow the peripheral blood blast reduction during the first cycle of therapy. When peripheral blasts have been reduced by at least 50%, we will perform a bone marrow, either day 4 or 8, to document if similar effects are occurring in the marrow as in the periphery. Also, excess cells obtained from the marrow at this early time point will be used to inform the impact of changes in gene signature from baseline marrow, which will have been obtained on the registration/pretreatment visit at day -4 to 0.

Usual supportive care transfusions will occur during the treatment cycle to maintain platelet count >10k at weekly assessments, and hematopoietic growth factors are not mandated as long as ANC >200/uL. Treatment outcome assessment will involve a bone marrow performed at day 15.

Assuming achievement of 50% or greater reduction in marrow blast score (cellularity x blast percentage) after 2 cycles, another cycle will be given. If the patient has had a response (CR, CRp or CRi) after 2 cycles, every attempt will be made to transition the patient to transplant.

However, if the patient is not a transplant candidate but the response after 2 cycles reaches the threshold 50% reduction, continuation of therapy cycles can continue with follow up bone marrow after the next 2 cycles as long as no evidence of peripheral progression occurs. Evidence for progression in the bone marrow would be a cue for discontinuation of therapy.

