2.1.3 Tertiary/Exploratory Objectives

- To measure the changes in TAK-659 plasma concentrations when given in combination with ixazomib.
- To quantitatively examine before, and at early timepoint of therapy, the primary mechanistic transcriptional drivers of these AMLs (HOXA and MEIS1), which are postulated to be extinguished by the drug combination, for their ability, when extinguished, to predict subsequent response
- To implicate Syk, Wnt pathway (ID1, JUN, FOXM1, β -catenin) and Wnt antagonists RUNX3 and Cullin 3 and EZH2 in responses affected by combination of TAK-659 and Ixazomib
- To use digital PCR technology to examine the participation of collaborating mutations on depth of remission for the class 1 and class 2 drivers

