11. Women of childbearing potential: A serum pregnancy test will be done at screening. A urine pregnancy test will be done predose D1 of all cycles, with negative results available prior to dosing. If a negative serum test is done within 3 days of C1D1, the C1D1 urine test will be waived.
12. Bone marrow biopsy and aspirate for disease burden (blast counts), cytogenetics, and cellular composition by flow cytometry will be done at screening. In addition, BM biopsies and/or aspirates will be done to assess disease response at Cycles 1, 2, and 4 between Days 15-21, provided the results are available before Day 1 of the next cycle. After Cycle 4, BM biopsy and/or aspirate assessment will be performed as clinically indicated based on changes in peripheral blood counts, or when it is needed to establish either CR or disease progression. NOTE: a BM biopsy is required only at screening. Residual and/or additional bone marrow samples will be requested for biomarker analysis. In cases when insufficient bone marrow aspirate is collected, peripheral blood will be collected and submitted per the instructions in the CLM.
13. Bone marrow will be done at C1D4 for the 1st 5 patients. Thereafter, BM timing (D4 vs 8) will be determined from the results in the first 5 patients.
14. Blood for PK plasma samples will be collected at: C1D1 (pre-dose, 2-4 hr post-dose), C1D15 (pre-dose, 2-4 hr post-dose), Cycle 2, 3, 4 Day 15 (pre-dose, post-dose anytime during clinic visit). Instruct patient to withhold study drug(s) for that day. The timing of the visit should be planned so that the pre-dose PK draw occurs near the same time as the previous day's dosing. When a blood sample coincides with the timing of an ECG, the ECG will be completed first. Refer to the CLM for detailed instructions on collection, processing, storing, and shipping of PK samples.
15. Whole blood for banking is to be collected at pre-dose C1D1. Serum and plasma for banking are to be collected at pre-dose C1D1 and at the 30-Day Safety Follow up visit. See CLM for collection, processing, labeling and shipping instructions.

8. STUDY CALENDAR: PHASE 2

Cycle = 21 days	Screen	Cycle 1				Cycles 2-4			C 3	Cycles 5+			Safety follow up	Long-term follow up
	-28 days ¹	D 1	D 4	D 8	D 15	D 1	D 8	D 15	D 22	D 1	D 8	D 15	30 days post Tx ²	Q month (±14) ³
REQUIRED ASSESSMENTS														
Informed consent ⁴ , Eligibility criteria	X													
Medical history, Disease characteristics	X	X												

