However, during phase 2, bone marrow aspirate and biopsy is a screening (baseline) procedure needed for the purpose of enrollment into the trial for both disease assessment and biomarker studies. In particular, bone marrow aspirate (BMA) or blood (if BMA not available) is needed to confirm the FLT-3 mutation status in marrow blasts, and therefore essential for patient assignment to either the FLT-3-ITD or WT group, as well as to determine the mutational burden by NGS for cooperating mutant epigenetic effectors. In cases for which the performance of this baseline procedure is difficult based on an individual patient's condition and a bone marrow aspirate/biopsy test has been performed within 28 days from Day 1 of Cycle 1, the site is encouraged to discuss the case with the Sponsor Investigator or delegate. In this circumstance, the site is required to investigate whether adequate residual material from the last bone marrow aspirate procedure remains available for collection and whether the tissue processing procedures for these remaining samples conform to the requirements of this trial for the

purpose of biomarker evaluation. If so, these samples should be collected and sent to the study-designated laboratory(ies).

- Note that a bone marrow biopsy is required only at screening. After screening, a biopsy that allows more bone marrow tissue to be examined should be performed (eg, when spicules are absent from the aspirate sample or a dry tap occurs) per local institutional practice at the time of disease assessment.

In addition, Phase I bone marrow aspirate and/or biopsy specimens (if needed) will be collected to assess pharmacodynamics (PD) at day 4 or day 8 (based on tempo of peripheral blood blast reduction), and to assess disease response between Days 15 and 21 and at the end of Cycle 1, Cycle 2, and Cycle 4, provided that the disease assessment is available before Day 1 of the following cycle during dose-escalation. The Cycle 2 marrow during dose-escalation/phase I is needed to gauge impact of marrow findings on dose-modifications if patients are not routinely in remission at this stage.

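### Phase I sections disagree on whether and on which day the early pharmacodynamic marrow is taken, which may select patients by early response or mix sampling day with ixazomib dose

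*Combined protocol and SAP*

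**What the plan says.** Several places govern the same early Cycle 1 marrow in Phase I.

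- Section 5.3.1: "When peripheral blasts have been reduced by at least 50%, we will perform a bone marrow, either day 4 or 8". The sample then has a research use: "excess cells obtained from the marrow at this early time point will be used to inform the impact of changes in gene signature".
- Section 8.3: the Phase I PD specimen is collected "at day 4 or day 8 (based on tempo of peripheral blood blast reduction".
- Section 7 (Phase I calendar), footnote 13: "Bone marrow will be done at C1D4 for the 1st 5 patients". It continues: "Thereafter, BM timing (D4 vs 8) will be determined from the results in the first 5 patients".
- Section 9.1 lists the same Phase I sample with no blast condition. It allows later patients to move to Day 8 depending on when the peripheral fall is seen.
- Section 9 places the on-treatment marrow at the end of three to four days of therapy.
- Section 8.1 says PD timing is set by the Schedule of Events and allows no flexibility.

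The sample has two uses. Section 2.1.3 wants the early change in HOXA and MEIS1 examined "for their ability, when extinguished, to predict subsequent response", and Sections 13.8 and 13.9 plan exploratory analyses of markers against remission and response. Section 5.3 also reviews PD after each dose cohort towards the recommended Phase II dose: "The criteria for defining an optimization of PD will be the reduction in more than one of the epigenetic drivers by 50" per cent, or a corresponding rise in RUNX3. That criterion names no sampling day. Section 13.9 summarises PD by patient, dose and genotype, but not by day.

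**The concern.** An analysis of whether an early marker change predicts remission needs patients who do not remit. If the marrow is taken only after blasts have halved, the marker is measured mainly in patients who are already responding. A patient with no circulating blasts at baseline could never meet the condition. Nothing downstream would repair this: Section 13.4 limits the PD population to patients with sufficient PD data, which it does not define, and Section 13.5 rules out imputation.

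The calendar avoids that selection but opens another problem. Dose levels are filled in order, so a change of day after the fifth patient is also a change of day across ixazomib dose. A larger early PD effect at a higher dose could then reflect more days on TAK-659.

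**Working it through.** The plan gives no figure for this analysis, so there is none to reproduce.

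**1. The rules side by side (Phase I)**

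| Section | Blast fall required? | Day |
|---|---|---|
| 5.3.1 | Yes, as worded (at least 50%) | 4 or 8 |
| 8.3 | Tempo of fall sets the day | 4 or 8 |
| 7, footnote 13 | No | 4 for first five, then 4 or 8 |
| 9.1 | No | 4 for first five, then possibly 8 |
| 9 | No | End of 3-4 days |
| 8.1 | No | Per Schedule of Events |

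Section 8.1 does not settle the matter, because the schedule it points to is footnote 13, which leaves the day open after patient five.

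**2. If Section 5.3.1 governs and decides whether to sample**

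Let p be the response rate, r the share of responders whose blasts halve, and n the share of non-responders whose blasts halve. Response rate among sampled patients = pr / [pr + (1 − p)n]. This exceeds p whenever r > n, so the direction is clear. The documents give neither r nor n, so the size is not.

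Illustration only, with assumed p = 0.40, r = 0.90 and n = 0.20 to 0.60 in 18 Phase I patients:

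- Responders: 18 × 0.40 = 7.2, of whom 7.2 × 0.90 = 6.5 are sampled.
- Non-responders: 18 × 0.60 = 10.8, of whom 10.8 × 0.20 = 2.2 to 10.8 × 0.60 = 6.5 are sampled.
- Response rate among those sampled: 6.48/8.64 = 75% down to 6.48/12.96 = 50%, against 40% overall.

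If the marker were unrelated to the blast fall given response, the main cost would be precision. If the marker tracks the blast fall, as the trial's hypothesis expects, the association itself is also distorted.

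**3. If the calendar and Section 9.1 govern and the switch to Day 8 is made after patient five**

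Inputs: three planned ixazomib levels (Section 5.2) and three or six patients per level under the 3+3 rules (Section 5.3). Assume that levels are filled in order, no patient is replaced and no lower level is expanded later. There are 2 × 2 × 2 = 8 size patterns. Day 4 samples per level are:

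| Size of cohort 1 | Cohort 1 | Cohort 2 | Cohort 3 |
|---|---|---|---|
| 3 | 3/3 | 2/3 or 2/6 | 0/3 or 0/6 |
| 6 | 5/6 | 0/3 or 0/6 | 0/3 or 0/6 |

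In every pattern one level mixes days and cohort 3 is all Day 8. If escalation ends after cohort 2, as one rule in Section 5.3 permits, the first two columns still differ in day.

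**4. What the day changes**

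Calendar assessments are made before dosing unless otherwise stated. A Day 4 marrow therefore follows 3 TAK-659 doses (Days 1-3) and a Day 8 marrow follows 7 (Days 1-7). Ixazomib has been given once (Day 1) in both cases. Take the 34.4-hour half-life in Section 1.4.2.1 and assume simple first-order accumulation:

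- Day 4 trough: 1 − 2^(−72/34.4) = 77% of steady state.
- Day 8 trough: 1 − 2^(−168/34.4) = 97% of steady state.

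**The case against.** The strongest reply is that only Section 5.3.1 links the marrow to a blast fall. Both calendars and Section 9.1 schedule it without that condition, and Section 8.1 gives the schedule authority. Section 5.3.1 does not say that the marrow is omitted if blasts do not fall. Read with Section 8.3, it may only choose the day. This stands. A reader might infer that the plan excludes non-responders from early sampling; the documents do not support that as a settled result. If the calendar is followed, the trigger loses no one.

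A reader might also extend the problem to the whole trial. That is not supported either. Section 5.3.1 sits under the dose-escalation rules and the tempo clause in Section 8.3 is confined to Phase I. In Phase II the day is set from Phase I results (Phase II calendar, footnote 13, and Section 9.1).

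A third inference would be that PD cannot be compared between doses at all. Section 9.1 schedules a Cycle 1 Day 15 biomarker marrow in both phases, and the PD criterion in Section 5.3 could be applied to it. That gives a common later time point. It does not replace the early sample that Sections 2.1.3 and 9 rely on.

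Finally, choosing the day from the first five patients is a deliberate design choice, the switch is optional, PD is one of five criteria listed in Section 5.3, and the marker-response work is exploratory. All of this limits the weight of the point. It does not remove the conflict between sections, and no section plans to account for sampling day.

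**Conclusion.** The concern holds as a conflict in the Phase I text, with a different consequence under each reading.

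- **Sections 5.3.1 and 8.3 followed:** sampling, or its day, depends on early response. The exploratory PD-response analysis may lose non-responders, including patients without circulating blasts. The direction follows if non-responders reach the fall less often than responders. The illustrative counts rest on assumed probabilities.
- **Calendar and Section 9.1 followed, with a switch to Day 8:** cohort 1 is all or mostly Day 4 and the highest planned level is all Day 8. The early comparison across cohorts then confuses ixazomib dose with 3 versus 7 prior TAK-659 doses. This needs an actual switch, no replacement, levels filled in order and, for the all-Day-8 level, cohort 3 to be opened.

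No primary analysis is affected. What is exposed is the early PD-response analysis and the PD criterion in choosing the recommended Phase II dose. A missed early marrow cannot be recovered later, so the text should be corrected.

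**What to change.** Bring Sections 5.3.1 and 8.3 into line with the calendar. Delete the 50% trigger and the tempo clause, so that every Phase I patient has the already scheduled early marrow whatever the blast count does. Align the timing statement in Section 9.

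Preferably use one early day for all Phase I dose cohorts and choose the Phase II day once Phase I is complete. The tempo of blast fall can still be studied: footnote 10 of the Phase I calendar asks for blood counts at least twice weekly in the first two weeks, with the blast percentage noted.

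If two days are kept, then:

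- record the actual day;
- do not pool or compare Day 4 and Day 8 values without stratifying by day;
- name the sampling day for the PD criterion in Section 5.3, or use the common Day 15 sample for the comparison between cohorts;
- report patients without an early marrow by response status.

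The cost is protocol wording and, under the preferred option, some loss of freedom to change the day during Phase I. No procedure is added beyond those already scheduled.
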